C.2. Overall Study Design: The R61 study will employ a randomized, double-blind, PBO-controlled, between-subjects design, coupling a standard Pavlovian fear conditioning paradigm during fMRI with an acute pharmacological challenge using oral dronabinol (THC) or PBO *prior to fear extinction* in PTSD patients and test recall of extinction learning 24 hr (proximal memory) and 1 week later (distal memory) when spontaneous recovery is expected to be robust. 78 PTSD participants will be randomized to 1 of 3 conditions: single doses of 5mg or 10mg of THC, or PBO, using covariate adaptive randomization¹¹⁸⁻¹²², in which a new participant is sequentially allocated to a treatment condition by taking into account baseline characteristics (e.g., CAPS-5, age, sex, race) and previous assignments of participants¹²³, with 26 PTSD participants per condition. However, because randomization does not guarantee comparability across groups, the groups will be compared to ensure reasonable similarity in the distributions of their baseline characteristics. The imbalance in covariate levels will be measured by a χ^2 goodness-of-fit test (for categorical covariates) or t-test (for quantitative covariates). Variables with significant group differences ($p<0.05$) will be included as covariates in primary analyses. Additionally, 26 healthy trauma-exposed controls (TEC; demographically matched) will be included and tested at comparable time points to separate the impact of trauma from the impact of PTSD. The TEC group will not receive THC, any drug-related monitoring, or undergo blood draws but will otherwise complete all phases of the

experiment. With the conservative anticipation that about 25% will fail to complete all parts of the study, we estimate about 20 PTSD subjects in each condition (60 PTSD participants in total) and 20 TEC participants in total. Participants will be recruited from the Detroit community and mental health clinics (**see 'Protection of Human Participants'**).

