C.2.4. fMRI: MR scanning at WSU will be performed on a 3.0 Tesla Siemens Magnetom Verio System using an industry-leading 32-channel head-coil for superior image quality. We will use a multi-band EPI sequence [similar to: TR = 2000ms; TE = 30ms; Flip = 73°; 128x128 matrix; FOV = 256 mm; 66 slices; 2.0 x 2.0 x 2.0 mm voxels], which we are currently using in PI [name]'s K01 project. A high-resolution structural image will provide precise anatomical localization. Whole-brain fMRI blood oxygen-level dependent (BOLD)-related signal measures will be acquired to measure task- and drug-related effects and to minimize susceptibility artifact (signal loss) at the medial temporal lobe (including the AMYG and the vmPFC)¹³³⁻¹³⁵.

C.2.5. General Statistical Approach: All analyses will use a conventional alpha level of 0.05 and all tests will be two-tailed. To evaluate the main effects, Analysis of Variance will be used for neuroimaging (i.e., BOLD percent signal change (PSC)) and peripheral measures of fear (e.g., SCR, US expectancy, SUDS, psychological/mood measures). We will also include covariates such as gender and childhood trauma/adversity

if found unbalanced and correlated ($r > 0.03$) with the outcome variable (e.g., MANCOVA, ANCOVA). If significant, multivariate analysis will be followed by univariate analysis, which if significant, will be followed-up with simple effects analysis (e.g., independent t-tests, paired t-tests). In addition to omnibus tests, planned comparisons will be used to test specific hypotheses such as THC dose (vs. PBO) on fear extinction in PTSD, as well as comparisons between THC doses; if there is no significant difference between THC doses we will examine potential positive trends with increasing dose. To evaluate relationships, Pearson correlations will be used along with scatterplots to examine the nature of the relationships. Hochberg step-down multiplicity adjustment will be used to control for all multiple comparisons¹³⁶. Confidence intervals and effect sizes will be also be calculated.

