Visit 2: Fear Acquisition: Approximately 1 hr for all participants. Participants are considered enrolled in the study once they have begun Visit 2 (if enrolled in PTSD group, participant will be randomized). Visit 2 will occur within 6 months of Visit 1. If more than 6 months have passed, we will re-do Visit 1 before the participant is able to complete visits 2 – 5.

Visit 3: Fear Extinction: Approximately 5 hr for those receiving a capsule (PTSD groups) or approximately 3 hours for those not receiving a capsule (TEC group)

Visit 4: Fear Extinction Recall and Fear Renewal Test (approximately 24 hr after extinction, but no more than 1 week later): Approximately 1.5 hr

Visit 5: Fear Extinction Recall, Fear Renewal Test, & Debriefing (approximately 1 week after extinction, but no more than 3 weeks later): Approximately 1.5 hr

Nature of Participant Population: Participants of both genders will be included in the study and the age range of participants will be from 18-60. Persons below 18 or above 60 are excluded because beyond this range age may influence response to the drugs. Furthermore, the relatively small age range is intended to reduce variation in performance on the behavioral task. There are no enrollment restrictions based upon race or ethnic origin. Candidates will undergo a structured clinical psychiatric interview¹⁵⁰ and complete questionnaires related to their general physical health, current medications, with a detailed section on current and lifetime drug and alcohol use. This study will not involve vulnerable populations.

The number of participants expected to participate is 104: 78 trauma-exposed participants with PTSD and 26 trauma-exposed participants without PTSD (TEC; demographically matched). There will be 3 experimental groups: PTSD participants will be assigned to 5mg of THC (n=26), 10mg of THC (n=26), or a placebo (PBO) (n=26). The 26 TEC participants will not receive THC or PBO. With the conservative anticipation 25% will fail to complete all parts of the study, we estimate 20 PTSD participants in each condition (60 PTSD participants in total) and 20 TEC participants will complete the study for a total of 80 participants. Participants will be recruited from the Detroit community and mental health clinics. We will enroll up to 175 participants to guarantee enough viable data and to account for participant drop out.

Recruitment

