Weekly meetings of the research staff of this study will be conducted that will include review of accrual, consenting procedures, protocol adherence, AEs, and quality control of all data obtained from the study in the previous weeks. Minutes of these meetings will be recorded, signed by the PI, and archived in a Regulatory Folder on the lab server. In addition, to participant-specific protocol deviation forms, protocol deviation will also be documented in a study-wide deviations log to facilitate monitoring and reporting to regulatory authorities. Similarly, AEs will be also documented in a study-wide AE log, which will be used to facilitate safety monitoring and identify AE trends across subjects, as well as overall AE reporting to the IRB and NIMH.

We will conduct a preliminary analysis during the early stages of data collection (once \approx 10% of the THC group has completed the study) to assess the efficacy and safety of the 5mg and 10mg doses and submit an amendment to adjust the dosing as needed (e.g. if 10mg shows significant improvement over 5mg, a further

increase in dosing [15mg] would be worthwhile). Our efficacy and safety metrics are based on the following criteria:

- 1) a. At least a medium effect size (Cohen's $d \geq 0.05$) between THC and PBO conditions in BOLD responses in *a priori* ROIs (vmPFC and/or HPC) and/or peripheral measures (SCR, US expectancy, SUDS) during recall of extinction learning; or
 - b. Relationship between change in BOLD responses in *a priori* ROIs (vmPFC and/or HPC) and/or change in peripheral measures (SCR, US expectancy, SUDS) during recall of extinction learning in THC (vs. PBO) is of at least a medium effect size ($r \geq 0.30$).
- 2) There will be no adverse events of more than mild severity that are rated as possibly, probably, or definitely related to acute administration of THC (more than PBO) in PTSD participants.

We will apply O'Brien-Fleming¹⁷⁹ type monitoring bounds as guidelines for the decisions regarding continuation or early termination of the trial. In addition to efficacy comparisons, frequency of AEs along with formal statistical comparisons of the frequency of AEs will be performed.

Reporting responsibility

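### The r > 0.03 covariate cut-off in C.2.5 screens out almost nothing and conflicts with the imbalance-only rule in C.2; the Aim 1 covariates should be fixed in advance

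*Combined protocol and SAP*

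**What the plan says.** Four places in the combined protocol and SAP bear on which covariates enter the Aim 1 models.

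- **C.2.5, General Statistical Approach.** "We will also include covariates such as gender and childhood trauma/adversity", but only "if found unbalanced and correlated ($r > 0.03$) with the outcome variable". Both conditions must hold. The section does not define imbalance, does not say on which participants the correlation is computed, and gives no reason for 0.03.
- **C.2, Overall Study Design.** After comparing the groups at baseline, "Variables with significant group differences ($p<0.05$) will be included as covariates in primary analyses". There is no correlation condition.
- **C.2.6, fMRI Analysis.** The region-of-interest model controls for potential confounds, with childhood trauma/adversity as the example and no threshold.
- **C.2.9, Aim 1 analyses.** The models control for potential confounds, which are not named.

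For comparison, criterion 1b of the interim assessment in the Data and Safety Monitoring Plan asks for a relationship that "is of at least a medium effect size" and gives r ≥ 0.30 as the figure.

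**The concern.** A correlation screen should keep covariates that predict the outcome and leave out those that do not. A cut-off of 0.03 cannot do that at this sample size, because sampling error alone produces larger correlations most of the time. As printed, the condition also has a sign. Taken at its word it would leave out a covariate with a strong negative correlation, and for a binary variable such as gender the result would depend on which category is coded 1.

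The covariate set for Aim 1 is at stake. C.2 and C.2.5 give two data-dependent rules that need not agree, and C.2.6 and C.2.9 do not say which applies. The analyst would have to choose between them after seeing the data, and the adjusted results for BOLD, ETI, US expectancy and SUDS could rest on different covariates.

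**Working it through.** **Inputs**

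- Cut-off: 0.03 (C.2.5). The plan derives it from nothing, so there is no figure to reproduce.
- Type of correlation: Pearson. C.2.5 says "To evaluate relationships, Pearson correlations will be used along with scatterplots"; I assume the screen uses it too.
- Sample size: C.2 says "we estimate about 20 PTSD subjects in each condition (60 PTSD participants in total) and 20 TEC participants in total", hence n = 60 or n = 80. The human-participants section says "The number of participants expected to participate is 104", which gives an upper check at n = 104.
- Imbalance level: p < 0.05, borrowed from C.2 because C.2.5 gives none (assumption).

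**Step 1. Variance explained at the cut-off.** 0.03² = 0.0009, or 0.09%.

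**Step 2. How often noise clears the cut-off.** With zero true correlation, t = r·√[(n − 2)/(1 − r²)] follows a t distribution on n − 2 degrees of freedom.

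- n = 60: t = 0.03 × √(58/0.9991) = 0.229. The two-sided tail is 0.820 and the upper tail 0.410.
- n = 80: t = 0.03 × √(78/0.9991) = 0.265. The two-sided tail is 0.792 and the upper tail 0.396.

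| Noise covariate passes if | n = 60 | n = 80 | n = 104 |
|---|---|---|---|
| magnitude of r exceeds 0.03 | 82.0% | 79.2% | 76.2% |
| signed r exceeds 0.03 | 41.0% | 39.6% | 38.1% |
| magnitude of r exceeds 0.30 | 2.0% | 0.7% | 0.2% |

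For scale, two-sided significance at 0.05 needs |r| of about 0.25 at n = 60 and 0.22 at n = 80.

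**Step 3. The whole rule, read as a magnitude.** Among randomised arms, a covariate shows imbalance at p < 0.05 about 5% of the time by chance. If imbalance is independent of the correlation with outcome (assumption), a noise covariate enters with probability 0.05 × 0.820 = 4.1% at n = 60, or 0.05 × 0.792 = 4.0% at n = 80. Imbalance alone would admit 5%. The correlation condition therefore removes 1 − 0.820 = 18% or 1 − 0.792 = 21% of what imbalance admits, about a fifth. The 5% does not carry over to comparisons with the TEC group, which is not randomised.

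**Step 4. The rule read literally, with its sign.** Simulation of 100,000 bivariate normal data sets per setting:

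| True correlation | Passes r > 0.03, n = 60 | n = 80 |
|---|---|---|
| −0.3 | 0.5% | 0.2% |
| +0.3 | 98.2% | 99.3% |

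**Step 5. C.2 against C.2.5.** A variable with a group difference at p < 0.05 and a correlation of 0.03 or less enters under C.2 and not under C.2.5. Under the literal reading the same holds for any such variable with a negative correlation. Conversely, because C.2.5 leaves imbalance undefined, a variable judged unbalanced at some p above 0.05 could enter under C.2.5 and not under C.2.

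**Step 6. Would a larger cut-off cure it?** In the same simulation, a covariate with true correlation 0.3 passes |r| > 0.30 in 51% of samples at n = 60. A screen at 0.30 keeps noise out but drops a useful predictor about half the time.

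**The case against.** The case for leaving this alone has four parts.

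**The rule also requires imbalance.** This is right. A reader might infer from the 80% figure that most noise covariates will enter the models. The documents do not support that: the rule is a conjunction, and under the assumptions above about 4% enter. One needless covariate costs one degree of freedom out of about 76 (80 participants less 4 groups) and does not bias the comparison between randomised arms.

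**The sign is only notation.** This is probably right. Criterion 1b in the Data and Safety Monitoring Plan also writes r ≥ 0.30 without bars, for relationships between BOLD and measures including US expectancy and SUDS. Hypothesis 1C expects activation to go with lower US expectancy and lower SUDS, so a negative correlation is the hoped-for result there, and the figure makes sense only as a magnitude. C.2.5 itself adds "All analyses will use a conventional alpha level of 0.05 and all tests will be two-tailed". A reader might infer that the plan shuts out every negatively correlated covariate. That follows only from C.2.5 alone and read literally; C.2 would still admit such a variable if its group difference reached p < 0.05.

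**The figure is a misprint for 0.30.** This is plausible. The same monitoring section prints Cohen's d ≥ 0.05 as a medium effect, so a misplaced decimal has a parallel. But nothing in the documents fixes the intended value, and Step 6 shows that 0.30 would be a poor screen in any case.

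**The harm is limited.** This also stands. Aim 1 compares THC with placebo among randomised arms, where leaving out a predictor mainly costs precision. Sex is one of the example balancing factors in the allocation, so it is less likely to be unbalanced among those arms.

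None of this answers the two remaining points: the condition does almost no screening, and C.2 and C.2.5 do not state the same rule.

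**Conclusion.** The point holds as a minor correction. The 0.03 cut-off explains 0.09% of variance, is cleared by noise in 82% (n = 60) or 79% (n = 80) of samples when read as a magnitude, and so reduces C.2.5 to something close to adjusting for whatever is unbalanced. That resembles the rule in C.2 without matching it, and the two can give different covariate sets for the same Aim 1 model.

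The pass rates assume a Pearson correlation, approximate normality, and the expected completer numbers. The 4% entry rate further assumes that imbalance means p < 0.05 and is independent of the correlation with outcome. The literal signed reading would be serious for an unbalanced covariate with a negative correlation (0.5% pass at a true correlation of −0.3, n = 60), but it is probably not what was meant and should be treated as wording to repair. The documents give no basis for saying that the THC-versus-placebo estimates would be biased, or that 0.30 was certainly the figure intended.

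**What to change.** Delete the correlation condition from C.2.5. Name one covariate set for all Aim 1 models, to be used whatever imbalance or correlation is observed: for example gender and the CTQ total, both already collected at screening, together with the allocation factors named in C.2 (CAPS-5, age, sex, race). Make C.2, C.2.5, C.2.6 and C.2.9 state this same rule, and do so before unblinding.

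Two details need a decision. Sex and gender overlap, so one of them should be chosen. CAPS-5 separates the PTSD and TEC groups by eligibility, so it suits the comparisons among the three randomised arms but not a model that also contrasts them with TEC.

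The cost is a short text change and a few degrees of freedom per model: two for gender and CTQ, plus one for each further continuous or binary factor and one fewer than the number of categories for race. No new data are needed.

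If the sponsor prefers to keep a screen, it should confirm the intended figure, write it as |r|, define imbalance, and say on which participants the correlation is computed. It should also recognise that |r| ≥ 0.30 would keep a covariate with true correlation 0.3 only about half the time at n = 60.

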Specific Aim 1 (R61 Primary Target Engagement): Assess effects of THC on recall of extinction learning and vmPFC and/or HPC activation in PTSD patients in a dose-finding study. *Hypothesis 1A: Relative to PBO, THC will dose-dependently increase vmPFC and/or HPC activation to a CS+E (vs. CS+U) during proximal (24 hr post-extinction learning) and/or distal (1 week post-extinction learning) recall of extinction learning in PTSD.* PCS (CS+E vs. CS+U) with ROIs (vmPFC, HPC) will be submitted to MANCOVA with Group (PTSD-5mg, PTSD-10mg, PTSD-PBO, TEC) as between-subjects factor and Recall (24 hr, 1 week) as within-subject factor, controlling for potential confounds. In addition to omnibus tests, planned comparisons will examine dose of THC on prefrontal-limbic engagement during recall of extinction learning in PTSD relative to PBO, and comparisons between THC doses; if there is no significant difference between THC doses we will examine potential positive trends with increasing dose. Similar analyses will be conducted using other variables of interest such as psychological measures, mood state, and drug effects. *Hypothesis 1B: Relative to PBO, THC will dose-dependently decrease peripheral measures of extinction recall (“extinction recall index” (ETI), US expectancy, SUDS) to the CS+E during a proximal and/or a distal test of extinction learning recall in PTSD.* These data will be submitted to MANCOVA with Group (PTSD-5mg, PTSD-10mg, PTSD-PBO, TEC) as between-subjects factor and Recall (24 hr, 1 week) as within-subject factor, controlling for potential confounds. Analyses will be comparable to that used to examine BOLD activation (*Hypothesis 1A*). *Hypothesis 1C: vmPFC and/or HPC activation will correspond with extinction recall success (i.e. higher ETI, lower US expectancy, lower SUDS).* Pearson correlation analyses will be used to correlate measures of BOLD activation (PSC) and peripheral measures (e.g., SCR, ETI, US expectancy) to the CS+E vs. CS+U within and across the two contexts/recall and renewal tests.

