R61 Power Analysis: We have conducted several power calculations in our previously published work used to determine the sample sizes proposed here. First, we have consistently found that an *n* of 14-16 healthy controls and an *n* of 14-16 PTSD patients provide adequate power to observe: 1) SCR differences and AMYG, vmPFC, HPC signal differences between groups during fear extinction and/or extinction recall; and 2) THC's effects on ETI and AMYG, vmPFC, and HPC activation in healthy controls. Similarly, normalization of corticolimbic responsivity to affective stimuli has been observed following exposure-based therapy in an *n* of 14 anxious patients¹⁴⁸ and following administration of a serotonin selective reuptake inhibitor (SSRI) with an *n* of 21 anxious patients¹⁴⁹. Given that the effect sizes tested within- and between-groups in previous fMRI studies have ranged between moderate to large (Cohen *d* = 0.7 - 1.5) with the anticipated cohort of 20 participants per group (PTSD-5mg, PTSD-10mg, PTSD-PBO, TEC), who complete the entire protocol with usable fMRI and SCR data, will confer >80% power to detect an effect size 0.72 or higher after necessary multiplicity adjustment.

PROTECTION OF HUMAN PARTICIPANTS

This Human Participants Research meets the definition of a clinical trial.

1. Risks to Human Participants

a. Human Participants Involvement, Characteristics, and Design

Involvement of Human Participants:

The total time commitment estimated per participant is 8.5-13 hr across all study visits. This is broken down below:

Visit 1: Screening & Study Entry: Approximately 3 hours for participants, unless a participant has already completed any of the screening assessments as part of another separate study. In this case, if the overlapping screening assessments were completed no more than 1 month prior to Visit 1 and the participant has signed HIPPA Authorization allowing us to access this prior data, Visit 1 will be approximately 1.5 hr.

Note: Due to the length and rigor of this initial screening process, it may sometimes be necessary for participants to complete screening measures across more than one visit (e.g., schedule conflicts). All screening measures will be completed within 2 weeks of the consent date.

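### The dose-level follow-up tests are not tied to the adjusted model: as written, they can drop covariates chosen for imbalance, and they ignore the factors used to balance the arms

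*Combined protocol and SAP*

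**What the plan says.** Allocation (C.2, Overall Study Design) is covariate-adaptive: "a new participant is sequentially allocated to a treatment condition by taking into account baseline characteristics", with CAPS-5, age, sex and race as examples. C.2 then brings a variable into the primary analyses only if the groups differ on it at p<0.05. C.2.5 (General Statistical Approach) brings in a variable such as gender or childhood adversity only if it is unbalanced and also correlated with the outcome.

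The models for Hypotheses 1A and 1B (C.2.9) are MANCOVAs on four groups (three PTSD arms and the trauma-exposed controls), with "Recall (24 hr, 1 week) as within-subject factor, controlling for potential confounds".

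Below the omnibus level there are two routes. C.2.5 says a significant univariate result "will be followed-up with simple effects analysis (e.g., independent t-tests, paired t-tests". In addition, C.2.5 and C.2.9 announce planned comparisons of THC dose with placebo and of one dose with the other. Neither section gives those comparisons a covariate set or an error term.

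The general rules are "All analyses will use a conventional alpha level of 0.05 and all tests will be two-tailed" and "Hochberg step-down multiplicity adjustment will be used to control for all multiple comparisons".

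**The concern.** The Study Group Assignment section says that the aim is to identify the minimum effective dose. The answer therefore lies in the pairwise dose comparisons, and the only tests named at that level are t-tests. Two separate things can go wrong.

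1. **Confounding and disagreement.** The covariates in the model are those the plan judged imbalanced. A bare t-test leaves out exactly those. An adjusted omnibus result and an unadjusted dose result can then point different ways, and nothing says which governs. Childhood adversity is a concrete case: it is named as a covariate but is not among the listed balancing factors.
2. **Efficiency.** When arms have been balanced on prognostic factors, a test that ignores those factors uses a standard error that is too large. It rejects less often than 5% under the null and misses real dose effects.

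**Working it through.** **Inputs from the document.** Two-sided alpha 0.05 (C.2.5); 26 allocated and about 20 completing per arm (C.2); d = 0.72 and a planning range of 0.7 to 1.5 (R61 Power Analysis).

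**Assumptions.** R², the share of outcome variance explained by the allocation factors: 0 to 0.30. r, the correlation of an imbalanced covariate with outcome: 0.3 to 0.45. Minimisation on four factors with a biased coin of 0.8, and random dropout. The document gives none of these.

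**The plan's own figure.** The R61 Power Analysis says that 20 per group "will confer >80% power to detect an effect size 0.72 or higher after necessary multiplicity adjustment". For an independent t-test the noncentrality is d·√(n/2) = 0.72·√10 = 2.277. With 38 df the critical value is 2.024 and power is 60.2% before any multiplicity adjustment. The stated figure does not reproduce for a between-arm comparison; that is a separate matter, but it shows there is no power to spare.

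**Pooled error alone.** With 57 df (three arms) power is 61.0%; with 76 df (all four groups) it is 61.3%. The gain is about 1 point.

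**Adjusting for the allocation factors.** The noncentrality becomes 2.277/√(1−R²), with 57−4 = 53 df and critical value 2.006. The simulated column is adjusted minus t-test power in simulated trials.

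| R² | Noncentrality | Power | Gain over 60.2% | Simulated gain |
|---|---|---|---|---|
| 0.05 | 2.336 | 63.1% | 2.8 points | about 2 |
| 0.10 | 2.400 | 65.4% | 5.2 | about 3 to 5 |
| 0.20 | 2.546 | 70.5% | 10.3 | about 9 to 10 |
| 0.30 | 2.721 | 76.2% | 15.9 | about 14 |

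At d = 1.0 the t-test has 86.9% power, and the gain is 3.6 points (R² 0.10) to 9.1 points (R² 0.30). At d = 1.5 the t-test has 99.6% and the gain is under 1 point.

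**True error of the unadjusted t-test.** Under perfect balance the limit is 2·[1 − Φ(1.96/√(1−R²))], which is 3.9%, 2.8% and 1.9% at R² = 0.10, 0.20 and 0.30. Real minimisation is imperfect, so the rate lies between this limit and 5%. Simulations gave 3.8 to 5.1%, 3.0 to 3.6% and 2.6 to 3.0%. Models that included all four factors stayed at about 4.5 to 5.9%.

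**What the plan's covariate rule would do.** In the simulations, including a factor only if it was imbalanced at p<0.05 picked up any balancing factor in about 1% of trials. The plan's own model then behaved like the unadjusted test: about 60% power and 2.6 to 2.9% error at R² = 0.30.

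**Dropping an imbalanced covariate.** Take a covariate outside the balancing scheme, with Zx its standardised difference between two arms and Zy that of the outcome. Under the null, Zy = r·Zx + √(1−r²)·e, with e standard normal. Given |Zx| > 1.96, the mean of |Zx| is 2·φ(1.96)/0.05 = 2.34, so Zy is shifted on average by 0.70 at r = 0.3 and 1.05 at r = 0.45. Integrating over Zx, the chance that |Zy| > 1.96 is 9.8% and 15.9%. Simulation with 20 per arm gave 9.6% and 15.3% for the t-test, against 4.9% in both cases for the comparison adjusted for that covariate.

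**The case against.** The t-tests are only an example, offered for simple effects after a significant univariate test. The next sentence of C.2.5 gives dose against placebo its own planned comparisons, and C.2.9 sets these directly after an adjusted MANCOVA; the authors may well have meant model contrasts. This stands in part. A reader might infer that the dose conclusions will certainly come from bare t-tests. The document does not say so; it leaves the point open, and that is the defect.

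A reader might also infer that the t-test throws away balancing factors that the model held, so that reusing the model's covariates would recover the lost power. It would not. Under the imbalance-only rules the model would usually omit those factors too, and reusing its covariates and error would recover only about 1 point.

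The power loss rests on an R² for a CS+E versus CS+U contrast that nobody has stated, and it is shown at the low end of effects that "have ranged between moderate to large (Cohen *d* = 0.7 - 1.5". This stands: the loss shrinks quickly with a larger d or a smaller R².

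Finally, a two-arm error term avoids assuming equal variances across all arms. That is true, and it costs about 1 point of power.

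**Conclusion.** The point holds in conditional form. The plan does not say which covariates or error term the dose-level tests use, and the only tests it names can contradict the adjusted model.

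- **Imbalanced covariate dropped:** a false-positive rate of about 10 to 16% for r = 0.3 to 0.45, but only in trials where that imbalance occurs. A reader might infer that the t-tests inflate false positives overall. They do not: averaged over all trials, the rate for a covariate outside the balancing scheme is 5%. The C.2.5 threshold of r > 0.03 also admits covariates too weak to matter.
- **Allocation factors ignored:** a true error of roughly 3 to 4%, and a loss of roughly 3 to 15 points of power at d = 0.72 with 20 per arm (about 60% against 65 to 76% analytically), if the factors explain 10 to 30% of variance. The loss is 0 to 3 points at 0 to 5%, and under 1 point at d = 1.5. A fixed loss, or a flat statement that the THC-placebo tests are conservative, is not supported.

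This does not account for the gap to the stated power of over 80%: even R² = 0.30 leaves the comparison near 76%.

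**What to change.** In C.2.5, replace the bracketed t-test examples with: *contrasts of estimated marginal means from the fitted model (5 mg v PBO, 10 mg v PBO, 10 mg v 5 mg; CS+E v CS+U within group), with the model's covariates and error term*. In C.2.5 and C.2.9, state that the planned comparisons are these contrasts.

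Add: *for comparisons among the PTSD arms, the model and its contrasts include the factors used in covariate-adaptive allocation, regardless of observed imbalance.* This sentence is what recovers the power. It also requires the plan to name those factors definitively, since C.2 lists them only as examples.

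The cost is two or three sentences, a few degrees of freedom, and an equal-variance assumption across arms that can be checked. It needs no extra data and places no burden on participants.
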